6.3 STUDY INTERVENTION COMPLIANCE

Subjects will complete a paper medication diary during the treatment period, recording the dates and times when post-operative pain medication is taken. Subjects will bring their bottles of post-operative medication to their Post-Op Day 14 clinic visit, at which time any remaining pills will be counted and recorded on the visit source document. This count will be reconciled with the medication log to calculate compliance.

6.4 CONCOMITANT THERAPY

For this protocol, a prescription medication is defined as a medication that can be prescribed only by a properly authorized/licensed clinician. Medications to be reported in the Case Report Form (CRF) are concomitant prescription medications, over-the-counter medications and supplements.

7 STUDY INTERVENTION DISCONTINUATION AND PARTICIPANT DISCONTINUATION/WITHDRAWAL

7.1 DISCONTINUATION OF STUDY INTERVENTION

Discontinuation from study intervention will mean discontinuation from the study, and those subjects will be considered screen failures and will be removed from the dataset. No further data will be collected from those who are determined to be screen failures.

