4.3 JUSTIFICATION FOR DOSE

The nasal cavity is innervated by sensory nerves via the trigeminal nerve. We believe using a standardized dose of bupivacaine 1.3% combined with 2mg preservative-free dexamethasone to areas on or around the nasal cavity that are innervated with sensory nerves will improve post-operative pain control results. A max amount of 20 mL will be injected into each study participant. The control group will receive no injection.

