5.3 SCREEN FAILURES

Screen failures are defined as participants who consent to participate in the clinical trial but are not subsequently randomly assigned to the study intervention or entered in the study. A minimal set of screen failure information is required to ensure transparent reporting of screen failure participants, to meet the Consolidated Standards of Reporting Trials (CONSORT) publishing requirements and to respond to queries from regulatory authorities. Minimal information includes demography, screen failure details, eligibility criteria, and any serious adverse event (SAE).

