7.2 PARTICIPANT DISCONTINUATION/WITHDRAWAL FROM THE STUDY

Participants are free to withdraw from participation in the study at any time upon request.

An investigator may discontinue or withdraw a participant from the study for the following reasons:

- If any clinical adverse event (AE), laboratory abnormality, or other medical condition or situation occurs such that continued participation in the study would not be in the best interest of the participant
- Disease progression which requires discontinuation of the study intervention
- If the participant meets an exclusion criterion (either newly developed or not previously recognized) that precludes further study participation
- Non-compliance with follow-up activities

Subjects who sign the informed consent form and are randomized but do not receive the study intervention may be replaced. Subjects who sign the informed consent form, and are randomized and receive the study intervention, and subsequently withdraw, or are withdrawn or discontinued from the study, will be replaced.

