8 STUDY ASSESSMENTS AND PROCEDURES

8.1 STUDY ASSESSMENTS

Subjects over the age of 18 who are undergoing functional endoscopic sinus surgery for chronic sinusitis as part of routine clinical care will be approached to participate in the study. Subjects screened and enrolled will follow the schedule of events provided in Section 1.2. The following evaluations will be performed:

Screening/Baseline:

- Obtain written informed consent
- Obtain demographic information
- Obtain medical history
- Obtain concomitant medication information
- Obtain routine vital signs, including height and weight
- Obtain routine nasal endoscopy
- Obtain/review routine CT scans of the sinus. This information may be obtained through review of existing data

Day of Surgery

- Randomization into the Treatment Group or the Control Group, as per measures outlined in Section 6.2
- Scheduled routine surgical procedure previously planned, based on subject's condition
- Study intervention administration to all subjects
- Post-operative medication diary will be given to all subjects
- Post-operative visual analog pain scale will be given to all subjects
- Assessment of adverse events
- Assessment of concomitant medications

Post-Operative Clinic Visit #1 (Day 10-21)

- Obtain routine nasal endoscopy
- Review of medication diary
- Review of visual analog pain scale
- Pain medication reconciliation via pill count

- Assessment of adverse events
- Assessment of concomitant medication

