8.2.4 TIME PERIOD AND FREQUENCY FOR EVENT ASSESSMENT AND FOLLOW-UP

The occurrence of an adverse event (AE) or serious adverse event (SAE) may come to the attention of study personnel during study visits and interviews of a study participant presenting for medical care, or upon review by a study monitor.

All AEs including local and systemic reactions not meeting the criteria for SAEs will be captured on the appropriate case report form (CRF). Information to be collected includes event description, time of onset, clinician's assessment of severity, relationship to study product (assessed only by those with the training and authority to make a diagnosis), and time of resolution/stabilization of the event. All AEs occurring while on study must be documented appropriately regardless of relationship. All AEs will be followed to adequate resolution.

Any medical condition that is present at the time that the participant is screened will be considered as baseline and not reported as an AE. However, if the study participant's condition deteriorates at any time during the study, it will be recorded as an AE.

Changes in the severity of an AE will be documented to allow an assessment of the duration of the event at each level of severity to be performed. AEs characterized as intermittent require documentation of onset and duration of each episode.

The Study Coordinator will record all reportable events with start dates occurring any time after informed consent is obtained until 7 (for non-serious AEs) or 30 days (for SAEs) after the last day of study participation. At each study visit, the investigator will inquire about the occurrence of AE/SAEs since the last visit. Events will be followed for outcome information until resolution or stabilization.

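### Section 7.1 relabels randomized participants as screen failures, removes them from the dataset and stops their follow-up, against Sections 5.3 and 8.2.4; Section 7.2 then allows them to be replaced

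*Protocol*

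**What the plan says.** Section 7.1 makes stopping the intervention equivalent to leaving the study. It then states that "those subjects will be considered screen failures and will be removed from the dataset. No further data will be collected".

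Section 5.3 defines screen failures as "participants who consent to participate in the clinical trial but are not subsequently randomly assigned to the study intervention" or not entered in the study. Even for them it asks for a minimal record that includes any serious adverse event.

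Section 7.2 is a separate rule on replacement. People who are "randomized but do not receive the study intervention may be replaced". Those who received the intervention "and subsequently withdraw, or are withdrawn or discontinued from the study, will be replaced". The listed reasons for withdrawal by the investigator include adverse events and non-compliance with follow-up. Section 7.3 counts loss to follow-up as withdrawal, so it falls under the same rule. Section 7.2 does not say whether a replaced person's data are kept.

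Section 8.2.4 requires events to be recorded "until 7 (for non-serious AEs) or 30 days (for SAEs) after the last day of study participation", and on-study adverse events to be followed to resolution.

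On the control arm, Section 4.3 says "The control group will receive no injection", while the day-of-surgery list in Section 8.1 includes "Study intervention administration to all subjects".

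**The concern.** A screen failure is by definition outside the randomized comparison, so leaving one out does no harm. Giving that label to someone already randomized turns a post-randomization exclusion into something that looks like pre-randomization attrition. The comparison is protected by randomization only if everyone randomized stays in it. If people leave for reasons linked to pain or to the injection, and others take their places, the arms that are compared are no longer the arms that were randomized.

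Two features make this more than a matter of wording. First, Section 7.1 stops data collection. An analysis plan can define populations, but it cannot analyse diaries, pill counts or adverse events that the protocol said not to collect. Second, the rule may not act equally on the two arms, because the protocol does not say what discontinuing the intervention means for a control who receives no injection.

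For safety the exposure is narrower. Section 5.3 keeps serious adverse events even for screen failures, so what can be lost from the analysed dataset is non-serious events and follow-up.

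**Working it through.** **Step 1: the texts side by side.** The protocol gives no figure to reproduce on this point, beyond 15 + 15 = 30 participants (Section 4.1), which is consistent.

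- *Order of events.* Section 8.1 lists randomization and then the intervention, both on the day of surgery. Section 7.1 does not use the word randomized, but anyone who discontinues the intervention has passed that step. The label contradicts Section 5.3.
- *Data collection.* Section 7.1 ends it. Section 8.2.4 requires it for a further 7 days (non-serious events) or 30 days (serious events), and Section 8.2.5 requires serious events to be followed until resolved, chronic or stable. Site staff cannot obey both.
- *Controls.* If the intervention means the injection (Section 4.3), Section 7.1 reaches only the injected arm, and under Section 7.2 every control is someone who did not receive the intervention and may be replaced. If it means the assigned arm (Section 8.1), both arms are covered. The protocol does not choose.

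**Step 2: how much it could matter.** All inputs except 15 per arm are assumed: no true effect; normal outcome with SD 1 (higher means more pain); two-sided 5% t-test; the k = 1, 2 or 3 participants with the highest removal score replaced in the same arm by new draws. One participant is 1/15 = 6.7% of an arm. The removal score is ρ × outcome + √(1 − ρ²) × noise, with ρ = 0, 0.3, 0.6 or 1.

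The expected bias is −ρ × (sum of the k largest expected values among 15 standard normal draws) / 15. Those values are 1.736, 1.248 and 0.948. For ρ = 1:

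- k = 1: 1.736/15 = 0.12
- k = 2: (1.736 + 1.248)/15 = 0.20
- k = 3: (1.736 + 1.248 + 0.948)/15 = 0.26

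Simulation of 200,000 trials per scenario gives the same biases and these false-claim rates (nominal 2.5% per side):

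| Removal from injected arm only | Bias in SD, k = 1 / 2 / 3 | False claims favouring injection |
|---|---|---|
| ρ = 0, unrelated to outcome | 0 / 0 / 0 | 2.5% |
| ρ = 0.3 | −0.04 / −0.06 / −0.08 | 3.1 / 3.7 / 4.0% |
| ρ = 0.6 | −0.07 / −0.12 / −0.16 | 3.9 / 5.3 / 6.5% |
| ρ = 1, worst outcomes removed | −0.12 / −0.20 / −0.26 | 5.5 / 9.0 / 12.5% |

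- *Control arm only:* the mirror image. For ρ from 0.3 to 1 the bias is +0.04 to +0.26 SD, and false claims favouring injection fall to between 2.0% and 0.5%.
- *Both arms equally:* no bias, 2.5% to 4.0% per side.

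**Step 3: safety example.** Suppose 2 of the first 15 injected participants have a non-serious event, both are removed and replaced, and the replacements have none. Exact (Clopper-Pearson) 95% intervals:

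- first 15 injected: 2/15 = 13.3% (1.7% to 40.5%)
- everyone ever injected: 2/(15 + 2) = 2/17 = 11.8% (1.5% to 36.4%)
- after removal: 0/15 = 0% (upper limit 21.8%)

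**The case against.** The strongest reply is that only Section 7.1 removes data, and that it is triggered by stopping a single injection given during surgery. Pain scores come afterwards, so removal would ordinarily happen before any outcome exists and could be at most weakly related to later pain. People who leave later fall under Section 7.2, which replaces them but nowhere deletes them. On this view the ρ = 0.6 and ρ = 1 rows, and the 0/15 example, apply the consequence in Section 7.1 to the population in Section 7.2. Silence on data retention in Section 7.2 is also something an analysis plan could settle. Finally, Section 6.1.2 and the synopsis describe both arms under the intervention heading, which favours reading the word as covering controls.

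Part of this stands. The number affected by Section 7.1 alone may be small, replacement does no harm if the original participants are retained, and the ρ = 1 row is an extreme case. But the protocol does not confine Section 7.1 to the operating room. Section 6.3 measures intervention compliance over a treatment period using the post-operative medication diary and pill count, and Section 7.2 lists a withdrawal reason that itself requires the intervention to be discontinued. An adverse event that stops the injection is directly a Section 7.1 case, so the safety example is possible. The reading by arm remains open because Sections 4.3 and 8.1 point in different directions. None of the reply removes the contradictions with Sections 5.3 and 8.2.4.

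**Conclusion.** The concern holds. As written, Section 7.1 excludes randomized participants and stops their data collection, contradicting the protocol's own definition of a screen failure and its adverse event recording rules. It is an explicit instruction, not a detail left for an analysis plan, and following it loses data that cannot be recovered. It must be corrected.

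The size cannot be derived from the protocol, which does not determine who is removed or from which arm. Under the assumptions above it ranges from no bias to about a quarter of an SD in either direction with one to three removals in one arm. The confident part of the conclusion is the contradiction and the irrecoverable loss; the simulated figures only show that, with 15 per arm, a few removals can matter.

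**What to change.** - **Section 5.3 and Section 7.1:** reserve the term screen failure for people never randomized. Delete the removal from the dataset and the stop on data collection in Section 7.1. Keep all randomized participants in the dataset and analyse them in their assigned arm with the data available.
- **Follow-up:** after the intervention is discontinued, continue diary, pill-count and adverse event collection unless the participant withdraws consent or is withdrawn under Section 7.2. In those cases keep what has already been collected.
- **Safety:** reconcile Sections 7.1 and 7.2 with the recording periods in Section 8.2.4, and count every injected participant.
- **Section 7.2:** state that any added participant is additional and does not substitute for the one who left.
- **Controls:** say how receiving or discontinuing the intervention is to be read for participants who get no injection.

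The cost is a change of wording, with the IRB review that the Statement of Compliance requires for any amendment. The dataset will contain a few incomplete records, and the number randomized may slightly exceed 30 if participants are added.

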7.2 PARTICIPANT DISCONTINUATION/WITHDRAWAL FROM THE STUDY

Participants are free to withdraw from participation in the study at any time upon request.

An investigator may discontinue or withdraw a participant from the study for the following reasons:

- If any clinical adverse event (AE), laboratory abnormality, or other medical condition or situation occurs such that continued participation in the study would not be in the best interest of the participant
- Disease progression which requires discontinuation of the study intervention
- If the participant meets an exclusion criterion (either newly developed or not previously recognized) that precludes further study participation
- Non-compliance with follow-up activities

Subjects who sign the informed consent form and are randomized but do not receive the study intervention may be replaced. Subjects who sign the informed consent form, and are randomized and receive the study intervention, and subsequently withdraw, or are withdrawn or discontinued from the study, will be replaced.

7.3 LOST TO FOLLOW-UP

A participant will be considered lost to follow-up if he or she fails to return for the post-operative scheduled visit within 21 days and is unable to be contacted by the study site staff.

The following actions must be taken if a participant fails to return to the clinic for a required study visit:

- The site will attempt to contact the participant and ascertain if the participant wishes to and/or should continue in the study.
- The investigator or his clinic staff will make every effort to regain contact with the participant (where possible, 3 telephone calls/portal messages/emails, and if necessary, a certified letter to the participant's last known mailing address or local equivalent methods). These contact attempts should be documented in the participant's medical record.
- Should the participant continue to be unreachable, he or she will be considered to have withdrawn from the study with a primary reason of lost to follow-up.

8 STUDY ASSESSMENTS AND PROCEDURES

8.1 STUDY ASSESSMENTS

Subjects over the age of 18 who are undergoing functional endoscopic sinus surgery for chronic sinusitis as part of routine clinical care will be approached to participate in the study. Subjects screened and enrolled will follow the schedule of events provided in Section 1.2. The following evaluations will be performed:

Screening/Baseline:

- Obtain written informed consent
- Obtain demographic information
- Obtain medical history
- Obtain concomitant medication information
- Obtain routine vital signs, including height and weight
- Obtain routine nasal endoscopy
- Obtain/review routine CT scans of the sinus. This information may be obtained through review of existing data

Day of Surgery

- Randomization into the Treatment Group or the Control Group, as per measures outlined in Section 6.2
- Scheduled routine surgical procedure previously planned, based on subject's condition
- Study intervention administration to all subjects
- Post-operative medication diary will be given to all subjects
- Post-operative visual analog pain scale will be given to all subjects
- Assessment of adverse events
- Assessment of concomitant medications

Post-Operative Clinic Visit #1 (Day 10-21)

- Obtain routine nasal endoscopy
- Review of medication diary
- Review of visual analog pain scale
- Pain medication reconciliation via pill count

- Assessment of adverse events
- Assessment of concomitant medication

8.2 ADVERSE EVENTS AND SERIOUS ADVERSE EVENTS

8.2.1 DEFINITION OF ADVERSE EVENTS (AE)

Adverse event means any untoward medical occurrence associated with the use of an intervention in humans, whether or not considered intervention-related (21 CFR 312.32 (a)).

8.2.2 DEFINITION OF SERIOUS ADVERSE EVENTS (SAE)

An adverse event (AE) is considered “serious” if, in the view of either the investigator or sponsor, it results in any of the following outcomes:

- Death
- A life-threatening adverse event (of note, the term “life-threatening” refers to an event in which the subject was at risk of death at the time of the event, rather than to an event which hypothetically might have caused death if it were more severe)
- inpatient hospitalization or prolongation of existing hospitalization
- a persistent or significant incapacity or substantial disruption of the ability to conduct normal life functions
- or a congenital anomaly/birth defect.

Important medical events that may not result in death, be life-threatening, or require hospitalization may be considered serious when, based upon appropriate medical judgment, they may jeopardize the subject and may require medical or surgical intervention to prevent one of the outcomes listed in this definition. Examples of such medical events include allergic bronchospasm requiring intensive treatment in an emergency room or at home, blood dyscrasias or convulsions that do not result in inpatient hospitalization, or the development of drug dependency or drug abuse.

8.2.3 CLASSIFICATION OF AN ADVERSE EVENT

8.2.3.1 SEVERITY OF EVENT

For adverse events (AEs) not included in the protocol defined grading system, the following guidelines will be used to describe severity.

- **Mild** – Events require minimal or no treatment and do not interfere with the participant’s daily activities.
- **Moderate** – Events result in a low level of inconvenience or concern with the therapeutic measures. Moderate events may cause some interference with functioning.
- **Severe** – Events interrupt a participant’s usual daily activity and may require systemic drug therapy or other treatment. Severe events are usually potentially life-threatening or incapacitating. Of note, the term “severe” does not necessarily equate to “serious”.

8.2.3.2 RELATIONSHIP TO STUDY INTERVENTION

All adverse events (AEs) must have their relationship to study intervention assessed by the clinician who examines and evaluates the participant based on temporal relationship and his/her clinical judgment. The degree of certainty about causality will be graded using the categories below. In a clinical trial, the study product must always be suspect.

- **Related** – The AE is known to occur with the study intervention, there is a reasonable possibility that the study intervention caused the AE, or there is a temporal relationship between the study intervention and event. Reasonable possibility means that there is evidence to suggest a causal relationship between the study intervention and the AE.
- **Not Related** – There is not a reasonable possibility that the administration of the study intervention caused the event, there is no temporal relationship between the study intervention and event onset, or an alternate etiology has been established.

8.2.3.3 EXPECTEDNESS

The Principal Investigator will be responsible for determining whether an adverse event (AE) is expected or unexpected. An AE will be considered unexpected if the nature, severity, or frequency of the event is not consistent with the risk information previously described for the study intervention.

8.2.4 TIME PERIOD AND FREQUENCY FOR EVENT ASSESSMENT AND FOLLOW-UP

The occurrence of an adverse event (AE) or serious adverse event (SAE) may come to the attention of study personnel during study visits and interviews of a study participant presenting for medical care, or upon review by a study monitor.

All AEs including local and systemic reactions not meeting the criteria for SAEs will be captured on the appropriate case report form (CRF). Information to be collected includes event description, time of onset, clinician's assessment of severity, relationship to study product (assessed only by those with the training and authority to make a diagnosis), and time of resolution/stabilization of the event. All AEs occurring while on study must be documented appropriately regardless of relationship. All AEs will be followed to adequate resolution.

Any medical condition that is present at the time that the participant is screened will be considered as baseline and not reported as an AE. However, if the study participant's condition deteriorates at any time during the study, it will be recorded as an AE.

Changes in the severity of an AE will be documented to allow an assessment of the duration of the event at each level of severity to be performed. AEs characterized as intermittent require documentation of onset and duration of each episode.

The Study Coordinator will record all reportable events with start dates occurring any time after informed consent is obtained until 7 (for non-serious AEs) or 30 days (for SAEs) after the last day of study participation. At each study visit, the investigator will inquire about the occurrence of AE/SAEs since the last visit. Events will be followed for outcome information until resolution or stabilization.

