1.2 SCHEDULE OF ACTIVITIES (SOA)

Procedures	Screening/ Baseline	Day of Surgery	Day 10-21
Informed consent	X		
Demographics	X		
Medical history	X		
Physical exam	X		
Vital signs	X		
Height & weight	X		
Nasal endoscopy	X		X
CT scans	X		
Randomization		X	
Administer study intervention		X	
Concomitant medication review	X	X	X
Adverse event review and evaluation	X	X	X
Pain diary		X	X
Visual analog scale	X	X	X
Pain medication reconciliation			X

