4 STUDY DESIGN

4.1 OVERALL DESIGN

Opioid analgesics are prescribed for moderate to severe pain disorders; however, there are contraindications and side effects that are common to all opioids. We hypothesize using local regional anesthetic after sinus surgery will reduce pain, therefore decreasing the need for post-operative opioid consumption.

This is a Phase 4, randomized, single-blinded, single-site, parallel-assignment intervention with a primary purpose of supportive care after functional endoscopic sinus surgery (FESS). It is anticipated that 30 subjects will be enrolled in this protocol. Potential subjects will be male or female adults over the age of 18 from the United States who undergo functional endoscopic sinus surgery (FESS) under the supervision of one surgeon.

Potential participants will be approached during their regularly-scheduled clinic visit about participation in the study. If they agree to participate, they will sign an informed consent form. During the baseline visit, demographic information, medical history, concomitant medications, vital signs, height, and weight will be collected. A routine nasal endoscopy will be performed to assess the need for surgical intervention, and routine CT sinus scans will be obtained and/or reviewed.

Participants will be randomized to one of the two following groups:

- **Treatment Group (n = 15):** participants will receive 20 mL of 1.3% bupivacaine with 2 mg dexamethasone injected locally in the location for sensory nerves of the sinus cavities and face during the FESS procedure
- **Control Group (n = 15):** participants will not receive regional anesthetic during the FESS procedure

Participants will have their scheduled functional endoscopic sinus surgery procedure. After surgery, participants will be given a pain diary to record their pain score on a scale of 1-10, and a place to record their use of opioids, as well as over-the-counter non-steroid anti-inflammatories such as acetaminophen and ibuprofen. Participants will record their scores and drug use daily for 10 days post-surgery. At their first post-operative clinic visit, the diary will be reviewed, and their opioid use will also be evaluated by counting the pills left on their prescription.

Data points/variables to be collected during the study could include the following, to be ascertained from the medical record and/or patient report:

- Name
- Medical Record Number
- Age
- Gender
- Type of surgery
- Duration of surgery

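### For adverse events that start and resolve at home, the timing detail required by 8.2.4 rests mainly on one look-back of 10 to 21 days, although a daily diary is already in use

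*Protocol*

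**What the plan says.** **What must be recorded.** Protocol 8.2.4 sets the content of the adverse event record: "Information to be collected includes event description, time of onset", and later in the same sentence "time of resolution/stabilization of the event". Two further requirements apply to particular kinds of event. Where severity changes, "Changes in the severity of an AE will be documented to allow an assessment of the duration of the event at each level of severity". Where an event comes and goes, "AEs characterized as intermittent require documentation of onset and duration of each episode".

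**How events are elicited.** The same section gives the method: "At each study visit, the investigator will inquire about the occurrence of AE/SAEs since the last visit". It also says that events may surface when a participant presents for medical care or when a monitor reviews the records.

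**When.** In the Schedule of Activities (1.2), the row "Adverse event review and evaluation" is marked at Screening/Baseline, Day of Surgery and Day 10-21. The visit list in 8.1 names adverse event assessment on the day of surgery and at the first post-operative visit, which is the only visit after surgery.

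**What participants write down at home.** Section 4.1 describes a diary, kept daily for 10 days, with a pain score and "a place to record their use of opioids, as well as over-the-counter non-steroid anti-inflammatories". Section 6.3 describes a paper medication diary with dates and times of pain medication. Neither description mentions symptoms or adverse events.

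**The concern.** The requirements in 8.2.4 are detailed: start, end, time spent at each severity level, and separate bouts. Detail of that kind is best captured close to the event. Here the participant is asked once, 10 to 21 days after surgery. Meanwhile the participant is already writing in a diary every day, but as far as the protocol describes it, only about pain and pills.

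Some of the reactions listed in 2.3.1, such as dizziness, tinnitus, blurred vision, restlessness, nausea and paresthesia, can be brief and need not lead to a clinic contact. If one occurs at home and passes, its timing has to be reconstructed at the visit.

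Two things depend on that timing. First, 8.2.3.2 makes temporal relationship one of the criteria for judging an event related to the intervention, so a vague onset weakens the causality assessment. Second, 2.3.3 anticipates only mild local reactions, and incomplete recording would tend to agree with that expectation.

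The person asking is the investigator. Section 4.1 calls the trial single-blinded without saying who is blinded, controls receive no injection (4.3), and no blinded assessor of adverse events is named. Section 4.2 also concedes that control participants may notice intact facial sensation and infer their arm, so the participant's account may not be free of arm knowledge either.

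**Working it through.** The protocol gives no figure to reproduce on this point. The check sets the requirement beside the means of meeting it, with simple arithmetic on the visit window.

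**Step 1. Requirement against source, for an event that starts and ends at home between surgery and the visit.**

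| Item required by 8.2.4 | Applies to | Scheduled source after the day of surgery |
|---|---|---|
| Start time | all adverse events | look-back at the Day 10-21 visit |
| End time | all adverse events | same look-back |
| Duration at each severity level | events whose severity changes | same look-back |
| Start and length of each bout | intermittent events | same look-back |

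An event on the day of surgery can be seen at that day's assessment. An event still present at the visit can be followed forward to its resolution, as 8.2.4 requires. The gap concerns events that are over before the visit.

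**Step 2. Length of the look-back.** Take the day of surgery as Day 0. The look-back runs from Day 0 to the visit: 10 − 0 = 10 days at the shortest and 21 − 0 = 21 days at the longest. The full days in between are 10 − 1 = 9 or 21 − 1 = 20.

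**Step 3. Reach of the existing diary.** The diary runs for 10 days. For a visit on Day 10 it covers every day in between. For a visit on Day 21 it leaves Days 11 to 20 uncovered, that is 10 of the 20 days, or 10/20 = 50%. A diary line that stopped with the present diary would therefore not cover the whole interval for later visits.

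**Step 4. Unscheduled sources.** Presentation for care and monitor review (8.2.4), and the medical record, from which 4.1 allows post-operative complications to be taken, can supply dates for events that reached a clinician or were written down. They do not help with a symptom that was neither reported nor recorded.

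**Step 5. Who elicits and who grades.** Section 8.2.4 assigns the inquiry to the investigator, and 8.2.3.2 assigns relatedness to the examining clinician. Neither is stated to be blinded or unblinded.

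**The case against.** The strongest reply is that nothing here is inconsistent. Section 8.2.4 states its own method, a question at each visit about the time since the last one, and the schedule follows it. A participant can give approximate start and stop dates when asked, so the schedule delivers the data with less precision. That stands: this is a choice of method that can be improved, not an error.

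Several stronger readings are tempting, and the protocol does not support them.

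- *That events are reviewed only on the day of surgery and at Day 10-21.* Section 1.2 also marks a baseline review. The single look-back is a statement about the period after surgery.
- *That bout-by-bout data are required for every event.* They are required for intermittent events, and duration by severity level matters only where severity changes.
- *That recall is the only source.* The medical record, presentation for care and monitor review also contribute, and events still open at the visit are followed forward.
- *That the diary has no place for events.* The form is not in the text at hand. The point rests on the descriptions in 4.1 and 6.3.
- *That the investigator is unblinded and prompts the arms differently.* The protocol does not say who is blinded, and 8.2.4 sets the same inquiry for everyone. Knowledge of the arm is a possibility, not a stated fact.
- *That the listed reactions fall in the days at home.* Section 2.3.1 gives no onset times. Some may appear on the day of surgery, when events are assessed.
- *That a between-arm safety comparison is compromised.* The objectives include no safety endpoint and the protocol states no formal comparison of harms.

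After these limits, one gap remains: events that begin and end at home and never reach a clinician.

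**Conclusion.** For adverse events that begin and resolve at home without a clinic contact, the timing required by 8.2.4 depends mainly on recall over 10 to 21 days, elicited by an investigator who is not stated to be blinded. This assumes that the diary form matches its descriptions in 4.1 and 6.3.

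The amount of under-recording or mistiming cannot be estimated from the protocol. A reader might take the share of days without a scheduled inquiry, 9/10 = 90% to 20/21 = 95%, as the share of events lost. It is not, because the visit inquiry looks back over those same days. One might also assume a recall rate and compute the chance that an event is recorded among the 15 treated participants. The protocol gives neither event risks nor recall rates, and such a figure would describe whether an event is noticed at all, not how well its timing and severity course are known.

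The point is a weakness in data quality. It merits a change because the instrument for better data is already in participants' hands.

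**What to change.** 1. Add one open, arm-neutral daily line to the existing diary, identical in both arms, for example: *Any new symptom today? Start, stop, did it limit your activity?* It should not name numbness or any other sensation that would cue the arm.
2. Continue that line until the Day 10-21 visit, beyond the present 10 diary days where the visit falls later.
3. State in 8.1 and 8.2.4 that this line is the primary participant-reported source for onset, resolution and episodes between surgery and the visit.
4. State there as well that at the visit the clinician reviews the line, asks the same open question in both arms, and grades severity and relatedness. The participant's entry informs the clinician's grading and does not replace it.
5. If the diary form already has such a line, no new line is needed. Say so in 8.1 and 8.2.4, and check that it runs until the visit.

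**Cost.** A diary reprint and IRB approval of the revised participant material, slightly more burden for participants, and more minor events for the clinician to review and grade. No extra visit is needed.
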